14.3 Estimates of study power

Sample sizes and design effect estimates:

Sample size was driven by the number of localities within the area in the country considered to be at-risk for malaria transmission and the number of index cases we expect will be identified within those localities during the study period. The overall, Target Area, and adherence evaluation samples are described above in section 14.1. To estimate power to detect differences in cumulative incidence we used sample size of 55,928 for the overall sample. To estimate power to detect differences in seroprevalence, we used sample size of 5400 for the Target Area sample based on the assumptions as described above. As noted we used harmonic means for locality size (cluster size) in our estimates of power and design effect rather than arithmetic means to estimate more conservatively and to reduce the impact of the few localities with large population sizes.

We conducted sample size calculations to determine our ability to detect a difference in the effectiveness of TPE compared to RACD on incidence. We used the equations suggested by Hayes and Moulton (Cluster Randomized Trials, CRC Press, 2009) to calculate sample size required to detect a difference between arms.

Calculations are made for differences in proportion and assuming a coefficient of variation of 0.9 based on census and surveillance data from September 2012 to March 2015 to estimate the number of localities with cases, index cases and cluster size as described above. The power calculations are sensitive to sample size, but—in our study—the cluster population size is fixed. Sample sizes for primary and secondary outcomes can be found in Table 9.

Primary outcome – Cumulative Incidence:

Our primary study outcome is cumulative incidence of passively detected malaria infections in the overall population of the randomized study area localities. If incidence in the RACD arm remains as it was during the 2012-2015 transmission seasons (during which RACD was the standard of care) then given the above assumptions, we would expect cumulative incidence in the RACD arm to be 0.4% or approximately 4 per 1000 persons. If this is the case, our study would have 80% power to detect a reduction in cumulative incidence to 0.2% or 2 per 1000 persons if at least 51 of the 77 study localities had at least one index case (Table 7). Should cumulative incidence in the RACD arm rise to 0.5%, the reduction to 0.25 or 2.5 per 1000 persons in the TPE arm would be detectable with at least 47 localities with at least one case. Should cumulative incidence in the RACD arm fall to 0.3%, reduction to 0.15% or 1.5 per 1000 persons in the TPE arm would be detectable with 57 localities with at least one case. Because of the clustered nature of the data and the variability in cluster size, we used the harmonic mean of the population size (656 per locality, or 41328 total population using the harmonic mean of locality population).

Secondary outcome of effectiveness – Seroprevalence:

In the end-line survey near the end of the study (expected mid 2017), non-index cases residing in Target Areas will undergo blood testing to measure seroprevalence. Index cases will also be included as long as they were not the first index case for a Target Area. The first index case will not be included as this person's malaria exposure was known to occur pre-intervention. The sample size for the seroprevalence measure is expected to be 5400. Based on preliminary data, we expect seroprevalence to be approximately 3% prior to any intervention.[6]

End-line seroprevalence for RACD was calculated based on an estimate that only 20% of individuals with infection will be detected by RACD and treated, leading to a 20% effectiveness of RACD, or a drop from 3.0% pre-intervention to 2.4% end-line seroprevalence. We believe that TPE will be more effective than RACD in reducing seroprevalence near the end of the study (expected mid 2017). Because of the clustered nature of the data and the variability in cluster size, we used the harmonic mean number of observations expected per locality (60) to generate the effective sample size for analytic power (3780). Using these assumptions, our study would have 80% power to detect a decrease in seroprevalence to 1.18% in the TPE arm if 63 of the 77 localities had at least one case (Table 8).

Secondary outcome on feasibility – Coverage:

For the feasibility outcome measure on coverage, estimates were based on the goal TPE coverage of 80%. This goal is based on modeling data which suggests at least 80% coverage is needed for MDA to be successful, as well as experience from some settings that have successfully interrupted transmission in the setting of MDA [8, 18]. If estimates of incidence in the TPE arm are accurate, approximately 66 index cases will be identified and 1782 individuals will be treated in the TPE-assigned Target Areas. If the true coverage is 80% coverage, we would have a 95% confidence interval between 77% and 83% with this sample size [38].

Secondary outcome on feasibility – Adherence:

To measure adherence to DP, we will perform a pill count in individuals residing in the first Target Area for each TPE locality each transmission season. We will have 5% absolute precision to detect 80% adherence when the sample size reaches 532. If adherence is lower than expected, we will still have 10% absolute precision to detect 50% adherence when the sample size 208.

Table 7. Detectable Reductions in cumulative incidence given different assumptions about Incidence in the RACD

# Total localities with at least one index case	# localities per arm	Number assessed per locality (n)		Cumulative Incidence		Km (coeff of variation)	Z beta	Power
		RACD	TPE	RACD (π_0)	TPE(π_1)			
47.0	23.5	656	656	0.500%	0.250%	0.9	0.84	80%
50.6	25.3	656	656	0.400%	0.200%	0.9	0.84	80%
56.6	28.3	656	656	0.300%	0.150%	0.9	0.84	80%
61.4	30.7	656	656	0.250%	0.125%	0.9	0.84	80%
68.5	34.3	656	656	0.200%	0.100%	0.9	0.84	80%
80.5	40.2	656	656	0.150%	0.075%	0.9	0.84	80%

Based on equation 4 from Hayes and Bennett International Journal of Epidemiology 1999;28:319-32

Assumes that population is only those in the EAs that have at least one case.

Sample size calculation based on harmonic mean of population size.

Table 8. Detectable reductions in seroprevalence given varying assumptions about prevalence in the RACD arm

# Total localities with at least one index case	# localities per arm	Number assessed per locality (n)		Outcome proportion		Km (coeff of variation)	Z beta	Power
		RACD	TPE	RACD (π_0)	TPE (π_1)			
46.6	23.3	60	60	3.00%	1.35%	0.9	0.84	80%
62.3	31.2	60	60	2.40%	1.18%	0.9	0.84	80%
49.3	24.7	60	60	2.00%	0.83%	0.9	0.84	80%
50.8	25.4	60	60	1.50%	0.57%	0.9	0.84	80%

Based on equation 4 from Hayes and Bennett International Journal of Epidemiology 1999; 28:319-326

Assumes we are including only persons in the target areas in the denominator but evaluating at locality level

Assumes 3 per 100 is the background seroprevalence

Table 9. Sample sizes for primary and secondary aims.

Outcome	Result*	Actual sample size (Effective sample size, based on harmonic mean in clusters)
Primary aim		
Incidence	0.4% (RACD) vs. 0.2% (TPE)	55,928 (41,328)
Secondary aims (effectiveness)		
Exposure (seroprevalence)	2.4% (RACD) vs. 1.18% (TPE)	5400 not including index cases (3720)
Infection prevalence	n/a	5600 includes index cases
Time to first post-intervention incident case	n/a	55,928 (41,328)

Outcome	Result*	Actual sample size (Effective sample size, based on harmonic mean in clusters)
Proportion of imported incident cases	n/a	55,928 (41,328)
Transmission potential	n/a	Genotyping estimated to be performed in 800 index cases** and 35 infections from follow-up cross sectional survey
Secondary aims (feasibility)		
Coverage in TPE Arm	80% (95% CI: 77%-83%)	1782
Adherence in TPE Arm	80%	532
Prevalence of SAEs related to treatment	n/a	5400 not including index cases (3720)
Acceptability	n/a	5400 not including index cases (3720)
Cost	n/a	10 Target Areas/arm

*for some secondary outcomes, power calculations were not performed however effective sample size is shown.

** 200 index cases will be from the study area but an estimated 600 DBS that are already collected as standard surveillance from other parts of the country will also be used to characterize the background genotypes/transmission potential in Swaziland, as it relates to the transmission potential in the study areas.

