Intervention	All individuals residing in study localities will receive vector control preventative measures as per program. In the TPE arm, all individuals in the Target Area will receive dihydroartemisinin-piperaquine (DP) once daily for 3 days with the first dose taken no later than 5 weeks from the index case presentation (goal within one week). Individuals in RACD Target Areas will be tested by RDT and taken to the nearest health facility for treatment as per program operating procedures.
Evaluation methods	
The primary outcome measure of incidence will be obtained routine surveillance data. Secondary outcomes will be measured through Target area-level surveys:
 
1) Blood surveys. At the time of enrollment of a new Target area in RACD arm and at study conclusion in both arms (LAMP, QT-NASBA, serology, genotyping). DBS collected in incident cases as part of routine surveillance will also be utilized for genotyping.
 
2) Feasibility measurements: Coverage of RACD or TPE in the target population, serious adverse event (SAE) reports, costing of every 10th RACD and TPE event, pill count in TPE arm.
 
3) Acceptability assessment. Focus group discussions with TPE study participants and RACD/TPE surveillance team members.

Sample size	The sample size is based on the number of study localities that experienced at least one incident case of malaria in the previous season. Within 77 randomized localities, we expect that 63 localities will have an incident case of malaria and receive an intervention. For the primary objective, we hypothesize that TPE will be more effective than RACD. At the current sample size the study is powered to detect a difference in cumulative incidence if incidence in the TPE arm is reduced 50% compared to the RACD arm. Incidence will be measured at the locality level and among the at-risk population, or all individuals in an enumeration area (EA) where at least one case was identified (expected to be approximately 55928 among total study population of 211,189, or a harmonic mean of 656 per locality (41,328 effective population). Secondary outcomes of seroprevalence and prevalence will be measured on individuals residing in Target Areas (total N=5400) with a harmonic mean of 60 persons receiving intervention per locality (3780 effective population).
Primary outcome	Incidence of malaria cases

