14.2 Outcome measures

Table 6. Outcome measures

Outcome	Indicator
Primary Aim	
Incidence	Cumulative incidence of all cases (Pf infection) identified by passive surveillance in the locality subsequent to the first reported case during the study period (not including additional cases found through RACD). Cases include both locally acquired and imported infections.
Secondary aims (effectiveness)	
Exposure (seroprevalence)	Seroprevalence to markers of recent exposure using ELISA in end-line survey samples taken from residents in Target Areas near the end of the study (expected mid 2017), excluding index cases detected through passive surveillance.
Infection prevalence	Prevalence of infection by LAMP and QTNASBA testing for gametocytes in LAMP positives in end-line survey samples taken from residents in Target Areas near the end of the study (expected mid 2017), including index cases detected through passive surveillance.
Time to first local post-intervention incident case	Time to first incident local case in the Target Area subsequent to the intervention. Target Areas that receive a repeat intervention will qualify to be included again at subsequent interventions.
Proportion of imported incident cases	Proportion of imported incident cases in the locality subsequent to the first reported case will be measured through passive surveillance. Additional cases found through RACD will not be included.
Transmission potential (by genotyping)	Microsatellite genotyping will be performed on samples collected from index cases as well as secondary cases.
Secondary aims (feasibility)	
Coverage	Proportion of persons residing within approximately 200m (TPE localities) or 500m (RACD localities) of the index case who consented to participate in the study and who completed the initial procedures for their study arm (finger prick for RDT in the RACD arm, initial dose of DP in the TPE arm)
Adherence	Proportion of persons who completed 3 days of therapy among all individuals initiated on DP in the TPE arm, as assessed by pill count
Prevalence of SAEs related to treatment	Proportion of subjects experiencing SAEs deemed possibly, probably, or definitely related to DP or AL, out of the total number of subjects enrolled
Acceptability	Qualitative assessment (See Section 10)
Cost	Cost per index case-level intervention, cost per case averted.

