For the primary analysis comparing incidence between the TPE and RACD arms, we will follow an intention-to-treat (ITT) approach. We hypothesize that cumulative incidence in the TPE localities will be lower than in the RACD assigned localities. For the initial ITT analyses, estimates of effect will be unadjusted for any variables other than intervention group. To check for possible contamination of effects by proximity to an index case treated with TPE, a second set of ITT analyses will be conducted adjusting for intervention group and distance of index case from an index case assigned to TPE. Outcomes are assessed at the individual level. Because of the clustered nature of the data, our modeling approach will also adjust for correlation of observations by locality for analyses using the overall sample and by locality and index case for analyses using the Target Area sample. Generalized estimating equations (GEE) will be used to perform the proposed primary analyses. GEE accounts for the correlation of persons within clusters and localities. GEE estimates are consistent even if the correlation structure is miss-specified, though GEE's statistical efficiency improves as the working correlation structure more closely approximates the actual correlation structure. Thus, several working correlation structures suitable for the study's design will be considered (e.g., unstructured, Autoregressive order 1, exchangeable). The QIC statistic will be used to select the final working correlation structure. Robust Huber-White "sandwich" standard errors will be used to obtain correct inferences even if

the chosen correlation structure remains slightly miss-specified. Alpha will be set at 0.05 for all planned comparisons.

Should the preliminary analyses reveal an imbalance in the baseline covariates between the TPE and RACD arms, a second set of models will be run for all primary analyses. Adjusted models will reweight the data (through inverse probability weighting, or targeted minimum loss based estimation) to recover effect estimates that reflect an equal distribution of baseline covariates.

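### The planning CV of 0.9 is close to Table 2's all-case value; removing each locality's first case, as the primary outcome does, raises it to about 1.15 and weakens the stated power

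*Combined protocol and SAP*

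**What the plan says.** Section 14.3 describes the power calculation as "assuming a coefficient of variation of 0.9 based on census and surveillance data", covering September 2012 to March 2015. It gives no working for the 0.9 and does not say which cases were counted. The control rate is set out as "we would expect cumulative incidence in the RACD arm to be 0.4% or approximately 4 per 1000 persons", and the effect is a halving of that rate. The cluster size is a harmonic mean: "we used the harmonic mean of the population size (656 per locality" with at least one case. On these inputs the section claims 80% power if 51 of the 77 localities have an index case; Section 14.1 expects 63. Table 7 varies the incidence from row to row but keeps k at 0.9 in every row.

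Table 6 (Section 14.2) defines the primary outcome as all passively detected cases in the locality, local and imported, "subsequent to the first reported case during the study period". Section 9.4 also leaves out the first case, but describes the incidence data as local cases only. Section 14.3 does not mention either exclusion.

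**The concern.** Subtracting one case from every locality with a case lowers the average rate but hardly changes the spread between localities. In Table 2, 23 of the 63 localities had exactly one case and fall to zero, while the largest goes only from 41 to 40. The relative spread must rise, so a k taken from all cases is too small for an outcome that leaves out the first.

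At the planning values, k supplies most of the variance in the Table 7 formula (64%, shown in the working). If it is set too low, the stated 80% power and the apparent margin of 63 expected over 51 needed are both too favourable. A null result would then be read with more confidence than the design supports.

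**Working it through.** **Inputs.** From Table 2: the 63 localities with at least one case, their local plus imported cases (333), and their expected at-risk population (55,928). Re-entered row by row, these match the printed totals and give a harmonic mean of 656.3, the plan's 656. From Section 14.3 and Table 7: p0 = 0.004, p1 = 0.002, n = 656, k = 0.9, z for power 0.84. "Alpha will be set at 0.05 for all planned comparisons" (Section 14.4) does not state sidedness. Two-sided (z = 1.96) is assumed, because it returns Table 7's numbers.

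**Step 1: reproduce Table 7.** The unmatched cluster formula is

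c = 1 + (1.96 + 0.84)² × V / (p0 − p1)², with V = p0(1 − p0)/n + p1(1 − p1)/n + k²(p0² + p1²).

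At k = 0.9: V = 6.073e-6 + 3.043e-6 + 0.81 × 2.0e-5 = 2.532e-5, so c = 1 + 7.84 × 2.532e-5 / 4.0e-6 = 50.6, as printed. The other five rows also match (47.0, 56.6, 61.4, 68.5, 80.5). The k term is 1.62e-5 of 2.532e-5, or 64%.

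**Step 2: estimate k from Table 2.** Poisson noise is removed from the variance of the locality rates:

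k = sqrt(s² − mean × average(1/n)) / mean, with average(1/n) = 0.0015237.

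The mean can be the pooled rate or the simple mean of locality rates.

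| Cases counted | s² of rates | Pooled rate | k (pooled) | Mean of rates | k (mean of rates) |
|---|---|---|---|---|---|
| All (333) | 3.709e-5 | 0.005954 | 0.89 | 0.005458 | 0.98 |
| First removed (270) | 3.820e-5 | 0.004828 | 1.15 | 0.003935 | 1.44 |

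For example, with the first case removed, pooled: sqrt(3.820e-5 − 0.004828 × 0.0015237) / 0.004828 = 0.005553 / 0.004828 = 1.15. The variance barely moves, while the mean falls by 19% (pooled) or 28% (mean of rates).

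**Step 3: how firm is it?**
- Other estimators with the first case removed: negative binomial 1.16, population-weighted 1.03.
- Within risk-rank strata, first case removed: 1.09 (pooled) to 1.37 (mean of rates), against 0.85 to 0.94 for all cases.
- Bootstrap of the 63 rows, pooled, first case removed: about 0.55 to 1.75. The paired shift from all cases to first-removed is 0.17 to 0.44 (pooled) or 0.30 to 0.70 (mean of rates), above zero in both.
- Without the one extreme locality (17 cases in 418 people): 0.77 to 1.11 with the first case removed, against 0.51 to 0.64 for all cases.
- Section 9.4's local-only definition, first case removed: 0.93 (pooled) to 1.32 (mean of rates).

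**Step 4: effect on power,** reading c as the total, as Table 7 does. Power = Φ( sqrt((c − 1)(p0 − p1)² / V) − 1.96 ).

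At k = 1.15: V = 9.116e-6 + 1.3225 × 2.0e-5 = 3.557e-5, so c = 70.7. At 63 localities: sqrt(62 × 4.0e-6 / 3.557e-5) − 1.96 = 2.641 − 1.96 = 0.681, so power is 75%.

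| k | Localities needed for 80% | Power at 63 | Power at 51 |
|---|---|---|---|
| 0.90 | 50.6 | 88% | 80% |
| 1.03 | 60.5 | 82% | 73% |
| 1.06 | 62.9 | 80% | 71% |
| 1.15 | 70.7 | 75% | 66% |
| 1.44 | about 100 | 60% | 51% |

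**Step 5: planning rate.** All cases give 333/55,928 = 0.595% over the Table 2 period of about three seasons. Two thirds of that is 0.397%, so the planned 0.4% also fits an all-case count. With the first case removed, the rate is 270/55,928 = 0.483% over that period. It is about 0.33% for two seasons if each case is assumed to be kept with probability 2/3 before the first is dropped. Using 0.483% in place of 0.4% moves power at k = 1.15 and 63 localities only from 75% to 77%.

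**The case against.** The strongest reply is that the origin of 0.9 is inferred. The sentence in Section 14.3 can be read as citing the surveillance data for the number of localities, index cases and cluster size, with 0.9 simply assumed. That stands: no text says 0.9 was computed from all cases, and it is only a near match to one of two estimators.

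The interval for k also contains 0.9, one locality drives much of its level, and the local-only wording in Section 9.4 gives a pooled 0.93. A reader might infer that 0.9 fits Table 2 only if every case is counted, or that it is plainly wrong. The documents support neither. They do support the direction: removing the first case raises k in both paired bootstraps and with the extreme locality left out, and every full-data estimate tried for the Table 6 outcome was 1.03 or higher.

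A reader might also set 1.44 against 0.9 and report a fall from 88% to 60%. That mixes estimators, because the one that gives 1.44 gives 0.98 for all cases. The fair counterpart of 0.9 is 1.15.

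Finally, the number of localities and their populations are fixed by geography. The correction therefore changes the stated power, not the design.

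**Conclusion.** The concern holds as a mismatch between a planning input and the outcome to be analysed. For the Table 6 outcome, Table 2 points to a k of about 1.15 (1.03 to 1.16 by most full-data estimators, 1.44 by one), imprecisely estimated, against the planned 0.9. Like for like and on Table 7's own reading, the cost is 88% to 75% power at 63 localities and 80% to 66% at 51. About 71 localities are needed, against 63 expected. Power of 80% survives at 63 localities only if k is no higher than about 1.06.

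This rests on two-sided alpha, the expected at-risk population as denominator, 2012-2015 heterogeneity carrying over to the trial, and Table 6 rather than Section 9.4 defining the outcome.

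A reader might be tempted to add the lower figures that follow from treating the formula's number as per arm, with 31.5 localities per arm: 59% at k = 0.9 and 46% at k = 1.15. The formula does give clusters per arm, and Table 7 prints that number as the total. This is a separate and larger error. The fall from 88% to 59% occurs at an unchanged k and has nothing to do with first cases, so it should not be counted here.

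**What to change.** - Recompute k and the planning rate from Table 2 on the primary outcome, with each locality's first case removed, and show the calculation and the estimator in Section 14.3.
- Add rows to Table 7 for k of about 0.9, 1.05 and 1.15, with 1.44 as a labelled upper bound, and note the influence of the one extreme locality.
- Restate the power and the claim that 51 of 77 localities are enough.
- Reconcile Table 6 (local and imported cases) with Section 9.4 (local cases only), since k depends on which applies.
- Correct Table 7's total-versus-per-arm labelling at the same time, and report its effect on power separately.

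The cost is a recalculation from data already in the protocol and a less favourable stated power. No localities, participants or changes in trial conduct are needed.

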115000	MANZINIMKHIWENIKa-KhuphukaKa-Bheni	1	8	0	8	2	2755	1408	1408
432000	LUBOMBODVOKODVWENIMalindzaSikhuph e	2	6	2	8	1	3526	2920	2293
404000	LUBOMBODVOKODVWENISitekiKhushweni	2	5	4	9	5	1773	799	799
349000	LUBOMBOTIKHUBAMaphungwaneMhlabub ovu	1	9	1	10	5	2172	1115	542
150000	HHOHHOMHLANGATANEMhlangataneZiny ane	1	12	2	14	6	5869	2328	1745
179000	HHOHHONTFONJENIEmvembiliMvembili	1	13	1	14	4	1456	689	689
440000	LUBOMBOLOMAHASHALomahashaLomaha sha	1	5	10	15	4	2485	1960	1573

420000	LUBOMBOLOMAHASHAShewulaNduma	1	13	4	17	7	3894	3043	3043
481000	LUBOMBONKILONGOBig- BendVillages, Ka- Goboyane	1	2	15	17	14	890	418	418
415000	LUBOMBOLUGONGOLWENISiteki TownSiteki Town	2	9	13	22	6	4796	2377	2377
436000	LUBOMBOLOMAHASHALomahashaNkalash ane	1	22	3	25	3	4154	2307	1886
473000	LUBOMBOSITHOBELAKa- NgcamphalalaMahlabatsini	1	35	6	41	20	5011	2222	2222
Totals:			236	97	333	108	211189	71661	55928

Unique Locality Name generated using names of Region, Constituency, Name1 and Name2 from Shapefiles.

Risk ranks 1 to 3 (highest risk being risk rank 1) assigned by NMCP according to historical and recent transmission.

Secondary case data based on LAMP data from reactive case detection, shown but not used for randomization as trigger for the study intervention, and primary outcome measure for the study is only based on incident cases.

Total population data from 2007 census data.

Historically at-risk population calculated as population of enumerations areas with recent and historical transmission.

Expected at-risk population calculated as population of enumerations areas with recent cases (sept 2012-mar2015).

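### The planning inputs (0.4% incidence, k = 0.9) appear to count each locality's first case, which the primary outcome excludes; both need restating on the same counts

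*Combined protocol and SAP*

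**What the plan says.** **Outcome.** Table 6 (section 14.2) defines the primary outcome as cumulative incidence of passively detected cases, local and imported, in the locality "subsequent to the first reported case during the study period". Section 9.4 also leaves out the first case, there for local cases. Section 2 gives the follow-up as two transmission seasons.

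**Planning rate.** Section 14.3 reasons from history: "If incidence in the RACD arm remains as it was during the 2012-2015 transmission seasons", then "we would expect cumulative incidence in the RACD arm to be 0.4% or approximately 4 per 1000 persons". On that rate, "our study would have 80% power to detect a reduction in cumulative incidence to 0.2% or 2 per 1000 persons", provided at least 51 localities have a case. It mentions no removal of first cases. Table 9 repeats 0.4% versus 0.2%.

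**Other inputs.** The calculation is described as "assuming a coefficient of variation of 0.9 based on census and surveillance data from September 2012 to March 2015", and "we used the harmonic mean of the population size (656 per locality"). Section 14.4 adds "Alpha will be set at 0.05 for all planned comparisons".

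**Source data.** Table 2 (section 4.3) lists every incident case by locality for September 2012 to March 2015. Its totals row reads "236 97 333 108 211189 71661 55928": 236 local and 97 imported cases, 333 in all, with an expected at-risk population of 55,928. Section 14.1 says that this population covers three seasons.

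**Sensitivity.** Section 14.3 and Table 7 already show 0.3% versus 0.15%, needing 57 localities, as what would apply if incidence fell.

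**The concern.** A locality's first case triggers the intervention and is not part of the outcome. In Table 2, 63 localities have at least one case, so 63 of the 333 cases (19%) are first cases, and 23 localities had exactly one case. A history like theirs would add nothing to the outcome as defined.

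If the planning rate was taken from all cases, it is too high for the outcome to be analysed. The same applies to k. Removing one case from every locality takes proportionally more from the low-count localities, so relative variation between localities increases. A lower rate and a larger k both raise the number of localities needed, and the power claim for the primary outcome rests on both.

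**Working it through.** **1. Check Table 2.** The 63 localities with a case sum to 333 cases and 55,928 people. The harmonic mean population is 656.3, which matches the stated 656.

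**2. Reproduce 0.4%.** Two of three seasons, all cases: 333 x 2/3 = 222, and 222 / 55,928 = 0.397%.

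**3. Reproduce k = 0.9.** Take each locality's rate (cases / at-risk population). From the variance of the 63 rates subtract the Poisson part (overall rate / 656.3). Then divide the square root by the overall rate.
- All cases: overall rate 333 / 55,928 = 0.005954; variance 3.709e-5; Poisson part 9.07e-6; k = sqrt(2.802e-5) / 0.005954 = 0.89.
- First cases removed: overall rate 270 / 55,928 = 0.004828; variance 3.819e-5; Poisson part 7.36e-6; k = sqrt(3.084e-5) / 0.004828 = 1.15.

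Dividing by the unweighted mean of the locality rates instead gives 0.98 and 1.44, a rise in the same direction.

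**4. Remove first cases from the rate.** Three ways, on two time bases. The expected number of localities with a case over a fraction f of the period is the sum of 1 - (1 - f)^cases over localities.

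| Basis | All cases | Minus 63 | Minus expected localities with a case | (333 - 63) x f |
|---|---|---|---|---|
| f = 2/3 (two of three seasons) | 222.0: 0.397% | 159.0: 0.284% | 222.0 - 54.2 = 167.8: 0.300% | 180.0: 0.322% |
| f = 24/31 months | 257.8: 0.461% | 194.8: 0.348% | 257.8 - 57.3 = 200.5: 0.358% | 209.0: 0.374% |

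Only the first row starts from the stated 0.4%. Like for like, the correction there is 0.075 to 0.113 percentage points.

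**5. Reproduce Table 7.** With z values 1.96 and 0.84, n = 656 and p1 = p0 / 2:

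c = 1 + (1.96 + 0.84)^2 x V, where V = [p0(1 - p0)/n + p1(1 - p1)/n + k^2(p0^2 + p1^2)] / (p0 - p1)^2.

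At p0 = 0.4% and k = 0.9, V = (6.07e-6 + 3.04e-6 + 1.62e-5) / 4.0e-6 = 6.329, so c = 1 + 7.84 x 6.329 = 50.6, as stated. All six rows reproduce (47.0, 50.6, 56.6, 61.4, 68.5, 80.5).

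**6. Apply the corrected inputs.** c is read as the total number of localities, as the table labels it. Power with 63 localities is Phi(sqrt(62 / V) - 1.96).

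| p0 | c, k = 0.9 | Power, 63 localities | c, k = 1.15 | Power, 63 localities |
|---|---|---|---|---|
| 0.400% (stated) | 50.6 | 88% | not applicable | not applicable |
| 0.284% | 57.9 | 83% | 78.0 | 71% |
| 0.300% | 56.6 | 84% | 76.7 | 72% |
| 0.322% | 55.0 | 85% | 75.1 | 73% |
| 0.358% | 52.7 | 87% | 72.8 | 74% |
| 0.374% | 51.9 | 87% | 72.0 | 74% |

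With k = 0.9, the table reaches 63 localities only when p0 falls to about 0.24%.

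**The case against.** **The derivation is inferred.** The documents never show how 0.4% was obtained, and routes that exclude first cases also round to it. One is 270 x 24/31 / 55,928 = 0.374%. Another uses the 134 index cases a year in section 4.4: (134 x 2 - 63) / 55,928 = 205 / 55,928 = 0.367%. This stands as a limit on certainty. Against it, neither route explains k = 0.9, whereas all-case counts explain both inputs. That evidence is indirect.

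**The third season is cut short.** Table 2 ends in March, while section 1.1 has transmission running from November to June. If monthly rates within a season are equal (an assumption), the data hold 2 + 5/8 = 2.625 seasons, and two seasons give 333 x 2 / 2.625 / 55,928 = 0.454% before any removal. This supports showing the 0.35-0.37% range beside 0.28-0.32%. The two should not be merged, because they correct different starting values.

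**The plan already covers 0.3%.** It does, at 57 localities against 63 expected. A reader might infer that the rate mismatch alone leaves the trial short of 80% power, or that the 0.4% row is plainly the wrong row. The documents support neither: with k = 0.9 and 63 localities, Table 7's own reading gives 83-87% across both ranges, and part of the range lies nearer 0.4% than 0.3%.

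**No stated calculation is wrong.** True. Table 7 reproduces, and 0.4% is an expressly conditional assumption. The fault is a mismatch between planning inputs and outcome definition.

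**Conclusion.** The mismatch is probable and should be corrected. The outcome excludes first cases, while the stated rate and the stated k both reproduce from counts that include them. After removal, expected RACD-arm incidence is about 0.30% (0.28-0.32%) on the basis that yields 0.4%, or 0.35-0.37% on the 24-of-31-month basis, and k is about 1.15.

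The rate alone has a small effect: about 52-58 localities instead of 51. The change in k matters more. With both corrected, the formula needs about 72-78 localities against 63 expected and 77 randomised, and power with 63 is about 71-74%.

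This rests on the inferred derivation, on continued 2012-2015 incidence, on the moment estimate of k from Table 2, and on the 63 localities. Section 14.1 attributes the 63 to two seasons, but Table 2 gives it over the full 31 months. At 54 localities with k = 0.9, power would be 82% at 0.4% and 78% at 0.3%, so only part of that shortfall comes from the rate.

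All these figures follow Table 7's own labelling. Whether its locality count is per arm or total is a separate issue.

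**What to change.** - In section 14.3, state the expected RACD-arm cumulative incidence after each locality's first case, with its derivation and time basis: about 0.30% (0.28-0.32%) for two of three seasons, or 0.35-0.37% for 24 of 31 months.
- Recompute k from the same counts. Changing the rate and keeping 0.9 would replace one mismatch with another.
- Restate the 80% power sentence, the base row of Table 7 and the 0.4%/0.2% entry in Table 9 from those inputs.
- If 0.4% and 0.9 already exclude first cases, show the calculation instead.

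The cost is a short recalculation from Table 2 and edits to a few figures. Design, conduct and outcome definition stay as they are. The restated power may fall below 80% at 63 localities and should then be reported as such.
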